#### 4.0 SYNOPSIS

Title	PERSEUS: A Phase 2 Proof of Concept Study Investigating the Preliminary Efficacy and Safety of Cenicriviroc in Adult Subjects with Primary Sclerosing Cholangitis (PSC)
Clinical Phase	2
Indication	Treatment of PSC
Objective(s)	
Primary Objective:
 
 
Evaluate effects of cenicriviroc (CVC) on serum alkaline phosphatase (ALP) over 24 weeks of treatment in adult subjects with PSC
 
 
Secondary Objectives:
 
 
To evaluate the safety and tolerability of CVC over 24 weeks in adult subjects with PSC
 

Study Design	
This is a single-arm, open label, proof of concept (PoC) study of CVC in adult subjects with PSC. The main objective of this PoC study is to assess changes in ALP both individually and as a group, over 24 weeks of treatment with CVC.
 
An informed consent form (ICF) will be signed prior to any screening activities. Screening will occur within 6 weeks before the Baseline Visit (Day 1). At the Screening visit, subjects will undergo all eligibility evaluations per the schedule of assessments. Subjects who meet all the eligibility criteria will be scheduled for a Baseline visit (Day 1) and enrolled in the study. The first dose of CVC will be given on-site at the Baseline visit. Subjects will return to the study site for on-treatment evaluations at Weeks 4, 8, 12, 16 and 24. Approximately 4 weeks after the last dose of study drug (Week 28), subjects will undergo follow-up evaluations. Subjects who discontinue study drug prior to completion of 24 weeks of treatment will be required to return to the clinic for an Early Discontinuation Visit.

Treatment Duration	24 weeks
Number of Subjects	Approximately 25 subjects in total, all of whom will be treated with open label CVC. If a subject discontinues from the study for any reason other than safety, a replacement subject will be considered.
Number of Study Centers	Approximately 10 centers in Canada and the United States
Target Population	Adult subjects with clinically diagnosed PSC

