Inclusion Criteria	
 
Adult male and female subjects aged 18-75 years with chronic cholestatic liver disease for at least 6 months
 
Clinical diagnosis of PSC as evident by chronic cholestasis of more than six months duration with either a consistent magnetic resonance cholangiopancreatography (MRCP)/endoscopic retrograde cholangiopancreatography (ERCP) showing sclerosing cholangitis, or a liver biopsy taken at any time consistent with PSC in the absence of a documented alternative etiology for sclerosing cholangitis. If diagnosis of PSC was made by histology alone, it must require the presence of fibro-obliterative lesions (i.e., onion skin lesions).
 
Subjects with or without Inflammatory Bowel Disease (IBD) are allowed. If subject has IBD, documented evidence of IBD either by prior endoscopy or in previous medical records, for <math>\geq 6</math> months. In addition, subjects will be required to enter the study with a Partial Mayo Risk score of 0-3, inclusively
 

	
 
4. In subjects receiving treatment with ursodeoxycholic acid (UDCA), therapy must be stable for at least 3 months, and at a dose not greater than 20 mg/kg/day
 
5. Serum ALP <math>\geq 1.5 \times</math> upper limit of normal (ULN)
 
6. 
 
7. Ability to understand and sign a written informed consent form (ICF)
 
8. Subjects receiving allowed concomitant medications need to be on stable therapy for 28 days prior to the Baseline Visit (see Section 9.3 for list of restricted medications), with the exception of UDCA in which subjects need to be on stable therapy for <math>\geq 3</math> months
 

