### 10.1 Screening Visit

Prior to any clinical procedures and evaluations, written signed informed consent must be obtained. Screening is to occur approximately 6 weeks before the Baseline visit (see Section 10.2).

Subjects who do not meet all eligibility criteria at Screening will be allowed to rescreen once. However, if a subject fails to meet eligibility criteria upon rescreen, he or she will remain ineligible for the study.

At Screening Visit, the following Screening procedures and assessments should be conducted:

■ [REDACTED]

[REDACTED]

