### 10.2 Baseline Visit (Day 1)

Subjects who have signed the ICF and meet all the eligibility criteria (see Sections [8.2](#) and [8.3](#)) will be enrolled in the study. If subjects are deemed eligible once results from the Screening visit are received, Baseline visit can take place immediately or approximately within 6 weeks after the Screening visit.

[REDACTED]

[REDACTED]

- [REDACTED]
- [REDACTED]
- [REDACTED]
- [REDACTED]
- [REDACTED]
- [REDACTED]
- [REDACTED]
- [REDACTED]
- [REDACTED]
- [REDACTED]
- [REDACTED]
- [REDACTED]
- [REDACTED]
- [REDACTED]
- [REDACTED]
- [REDACTED]
- [REDACTED]
- [REDACTED]
- [REDACTED]
- [REDACTED]
- [REDACTED]
- [REDACTED]
- [REDACTED]
- [REDACTED]
- [REDACTED]

[REDACTED]

[REDACTED]

[REDACTED]

[REDACTED]

[REDACTED]

[REDACTED]

[REDACTED]

[REDACTED]

[REDACTED]

[REDACTED]

[REDACTED]

[REDACTED]

[REDACTED]

[REDACTED]

[REDACTED]

[REDACTED]

[REDACTED]

[REDACTED]

[REDACTED]

[REDACTED]

[REDACTED]

[REDACTED]

- █ [REDACTED]
- █ [REDACTED]

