## 1.6 STUDY PROCEDURES

Screening will occur within 6 weeks before the baseline visit. Subjects enrolled under Amendments 1 and 2 were also required to have a pre-baseline visit, which was removed in Amendment 3. Eligible subjects will be seen at baseline (Day 1), (Week 2), Week 4, Week 8, Week 12, Week 16, and Week 24. A safety follow-up visit will be conducted at Week 28 ( $\pm 3$ ) days (i.e., 4 weeks after last intake of study medication) or at the time of early termination (if a subject discontinues the study early). On visit days, subjects will be asked to come in to the clinic while fasting. Blood samples will be collected before dosing. Subjects will be required to bring in study medication on the days of clinic visits, and dosing will be conducted on-site with a morning snack.

Data will be collected as follows:

- █ [REDACTED]
- █ [REDACTED]
- █ [REDACTED]
- █ [REDACTED]
- █ [REDACTED]
- █ [REDACTED]
- █ [REDACTED]

†

[Redacted]

[Redacted]

[Redacted]

[Redacted]

[Redacted]

[Redacted]

[Redacted]

[Redacted]

[Redacted]

[Redacted]

[Redacted]

[Redacted]

[Redacted]

[Redacted]

[Redacted]

[figure not shown]
[Redacted]

[figure not shown]
[Redacted]

[Redacted]

[Redacted]

[Redacted]

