#### 3.4 BASELINE VALUES

The baseline value will be defined as the last nonmissing value on or before the baseline visit (Day 1).

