### 7.1.1 Pre-treatment Change per Week with On-treatment Change per Week

Also a comparison of *pre-treatment change per week with on-treatment change per week* will be made through an estimate specification and the corresponding 95% confidence interval will be reported. To this end, a similar linear mixed-effect repeated measure model will be fit with change from baseline at the visit as the dependent variable, visits (baseline, Weeks 4, 8, 12, 16, and 24) as fixed factors, baseline score and baseline score-by-visit interaction as covariates, the visit nested within subject and subject as a random effect to model correlations among the within-subject repeated measures. A compound symmetry structure will be used initially in the model for the correlation pattern among the repeated measures. If this does not converge, then other covariance structure, for example, the spatial power covariance structure for unequally spaced time intervals will be used to model the repeated assessment over time. Denominator degrees of freedom will be estimated using the Kenward-Roger method.

Pre-treatment change from baseline is defined as follows:

$$\text{screening value} - \text{baseline value}$$

For multiple t-test, pairwise comparisons based on the Bonferroni adjusted t-test would produce comparisons of the group means for *on-treatment change* from baseline at the visit *back to pre-treatment change*. Through this model, two-sided 95% confidence intervals will be produced for comparisons of the group means at the visit (*on-treatment change*) back to the first time point (*pre-treatment change*).

Percent changes in ALP from baseline will be summarized using descriptive statistics for the respective pre-treatment and on-treatment visits.

The ALP raw values and the percent change from baseline in ALP at each visit will be summarized descriptively by visit: before treatment (screening, baseline) and during treatment (Weeks 2, 4, 8, 12, 16, and 24).

Descriptive comparisons will be made for the following:

- Subjects with a history of IBD vs. no history of no IBD at screening
- Subjects who received UDCA for at least 3 months before screening vs. who have not received UDCA for at least 3 months before screening

Figures for the percent changes in ALP from baseline by visit will also be presented.

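### SAP 7.1.1 compares on-treatment ALP with the Screening value on which subjects were selected, so the contrast shows a fall even if CVC does nothing

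*SAP*

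**What the plan says.** **Selection.** Inclusion criterion 5 requires serum ALP of at least 1.5 × ULN. It names no visit, but the Protocol Synopsis states: "At the Screening visit, subjects will undergo all eligibility evaluations per the schedule of assessments". Protocol 10.2 adds: "If subjects are deemed eligible once results from the Screening visit are received, Baseline visit can take place immediately". Protocol 10.1 gives a second chance: "Subjects who do not meet all eligibility criteria at Screening will be allowed to rescreen once". The Synopsis has clinical laboratory tests, including ALP, drawn again at Baseline.

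**Pre-Baseline visit.** SAP 1.6: "Subjects enrolled under Amendments 1 and 2 were also required to have a pre-baseline visit, which was removed in Amendment 3". The pre-treatment visits in the readable ALP-by-visit summary of SAP 7.1.1 are screening and baseline only.

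**Baseline.** SAP 3.4 takes the last nonmissing value up to and including Day 1.

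**Comparison.** Under a title that speaks of change per week, SAP 7.1.1 writes "Pre-treatment change from baseline is defined as follows", followed by screening value minus baseline value, with no division by time. It then plans Bonferroni-adjusted t-tests and two-sided 95% intervals for "comparisons of the group means at the visit (*on-treatment change*) back to the first time point (*pre-treatment change". The visit factor listed for the model runs from baseline to Week 24 and has no Screening level.

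**The concern.** A value that had to clear a lower threshold is, on average, above the subject's own long-run level. The next draw tends to be lower without any treatment. A rescreen strengthens this, because a subject who missed the threshold gets a second chance at a favourable fluctuation.

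The trial has one arm and each patient is his or her own control, so a comparison of treated with untreated ALP change will be read as evidence about the drug. If its expected value is not zero when the drug does nothing, its confidence interval does not mean what a reader will take it to mean. The direction also depends on details that the SAP leaves open (sign, time divisor, which Screening value), so the reader cannot tell which way the result leans.

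**Working it through.** **Step 1: the planned effect.** Protocol 12.1 assumes a true mean improvement of 30% over 24 weeks, SD 25%, n = 25, lower 95% limit above 15%, power 0.80. The noncentrality is (30 − 15)/(25/√25) = 3, and the noncentral t with 24 df gives power 0.82, so the plan's figure reproduces and is not in dispute. The planned weekly rate is 30%/24 = 1.25%.

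**Step 2: what the contrast estimates.**

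(visit − baseline) − (screening − baseline) = visit − screening.

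The model terms do not undo this. With complete data and a baseline-by-visit term, each visit's adjusted mean at the average baseline equals its raw mean.

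**Step 3: expected value with no drug effect.** The documents give no within-subject ALP variability and no distribution of candidates, so these are assumptions. True ALP is log-normal with median M (in × ULN) and between-subject log-SD 0.45. Draws have independent within-subject log-SD w. Entry needs Screening ALP ≥ 1.5 × ULN. Without rescreening:

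- t = √(0.45² + w²) and a = (ln 1.5 − ln M)/t
- mean log excess of Screening = (w²/t) × φ(a)/[1 − Φ(a)]
- expected fall = 1 − exp(−excess)

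Central case, M = 2.2 and w = 0.20: t = 0.492, a = −0.778, φ(a)/[1 − Φ(a)] = 0.295/0.782 = 0.377. The excess is (0.04/0.492) × 0.377 = 0.0306 and the fall is 3.0%.

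Simulation (3 million candidates per row, geometric means) agrees and adds the rescreen:

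| M | w | Fall, no rescreen | Fall, one rescreen |
|---|---|---|---|
| 1.8 | 0.10 | 1.2% | 1.7% |
| 1.8 | 0.25 | 6.9% | 8.5% |
| 2.2 | 0.20 | 3.0% | 3.9% |
| 3.0 | 0.10 | 0.3% | 0.4% |
| 3.0 | 0.25 | 2.1% | 2.6% |

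A wider grid (median down to 1.5 × ULN, between-subject log-SD 0.4 or 0.6, within-subject CV up to 30%) reaches 13.0% without and 15.0% with a rescreen. In every setting the expected geometric change from Day 1 to a later visit is 0.0%, apart from simulation error.

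**Step 4: the same artefact as a rate.** Screening may be up to 6 weeks before Day 1; a 4-week run-in is an assumption.

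- 6 weeks: 3.0/6 = 0.50 to 3.9/6 = 0.65% per week
- 4 weeks: 3.0/4 = 0.75 to 3.9/4 = 0.98% per week

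In time order (baseline minus screening) this is a fall before treatment, equal to 40% (0.50/1.25) to 78% (0.975/1.25) of the planned rate, and it would be set against CVC. With the SAP's sign (screening minus baseline) it is a rise, and it would be credited to CVC.

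**The case against.** The strongest reply is that little depends on this comparison. SAP 1.3 calls the study's main objective exploratory, the analysis is mainly descriptive, and the sample-size argument rests on Baseline to Week 24. No readable decision rule uses SAP 7.1.1. The size rests on assumed inputs and is small if most candidates sit well above the threshold. Upper Screening limits on AST, ALT and bilirubin may partly offset it. At n = 25 in the central case, the 95% half-width for the Screening-to-Day 1 change is about 11.5 log-points, roughly three times the artefact. All of this stands, and it limits the importance of the point. It does not remove it: the shift is systematic and the contrast is reported with confidence intervals.

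A reader might infer three stronger things that the documents do not support.

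- That the primary endpoint is biased. It uses a separate Day 1 draw, taken before the first on-site dose. Only a missing Day 1 ALP brings Screening in, and SAP 3.4 already places a pre-Baseline value ahead of Screening.
- That the run-in is the only untreated observation. Amendment 1-2 subjects had a pre-Baseline visit, there is an off-drug Week 28 visit, and the Synopsis plans historical comparisons.
- That pre-Baseline to Baseline should replace the reference. The number of such subjects is not given. The Amendment 3 summary names AST, ALT and bilirubin as the repeated tests, so ALP at that visit is likely but not shown. With w = 0.20 and an assumed 8 or 12 subjects, the 95% half-width is about 24 or 18 log-points, far wider than the 3-4% being removed.

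**Conclusion.** The point holds for the SAP 7.1.1 comparison. As written, each contrast is change from a selected value and has a non-zero expectation under no effect: about 3-4% in the central case and roughly 0.3-8.5% over medians of 1.8-3 × ULN and within-subject log-SDs of 0.10-0.25. As a rate this is about 0.5-1.0% per week over a 4-6 week run-in, against a planned 1.25%. The direction favours CVC as visit versus Screening and works against it as a time-ordered rate.

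The cancellation follows from the SAP's own definition. The size rests on the assumed candidate distribution, the assumed variability and independent errors between draws. That ALP selection took place at Screening is inferred from the Synopsis and Protocol 10.2. Parts of SAP 7.1 are redacted; the readable text does not mention regression to the mean. The primary percent change from Day 1 stands, apart from any subject whose baseline falls back to Screening.

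**What to change.** In SAP 7.1.1:

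1. Report the Screening-to-Baseline change, and any contrast with it, as descriptive only and labelled as affected by selection on Screening ALP. Do not use its 95% interval as evidence of a CVC effect. Base inference on change from the Day 1 value.
2. Define the pre-treatment rate in time order: baseline minus screening, divided by the actual weeks between the two draws. State which Screening value is used after a rescreen.
3. If ALP was measured at the pre-Baseline visit, add it to the ALP-by-visit table and show the pre-Baseline-to-Baseline change in Amendment 1-2 subjects as a supportive sensitivity analysis, not as the replacement reference.

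For the primary endpoint, add a sensitivity analysis that excludes any subject whose ALP baseline is the Screening value.

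The cost is SAP wording and a few extra displays, with no new visits or samples. The supportive run-in comparison loses its inferential status, and the pre-Baseline subset may be small and imprecise.

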## 7.2 SECONDARY EFFICACY ENDPOINTS

Secondary efficacy endpoints include the following:

- The proportion of patients who achieve ALP normalization (ALP values outside of the central laboratory reference range at baseline, but within the central laboratory reference range at each visit according to the central laboratory reference ranges) at each visit, with secondary endpoint defined at Week 24
- The proportion of patients who achieve a decrease in ALP of  $<1.5 \times \text{ULN}$  at each visit with secondary endpoint defined at Week 24
- The proportion of patients who achieve a 50% decrease in ALP from baseline at each visit, with secondary endpoint defined at Week 24

[REDACTED]

[REDACTED]

[REDACTED]

[Redacted text block]

[Redacted text block]

■ [Redacted text block]

[Redacted text block]

■ [Redacted text block]

■ [Redacted text block]

■ [Redacted text block]

■ [Redacted text block]

■ [Redacted text block]

[Redacted text block]

[Redacted text block]

Statistical Analysis Plan

---

[REDACTED]

[REDACTED]

[REDACTED]

[REDACTED]

[REDACTED]

[REDACTED]

[REDACTED]

[REDACTED]

[REDACTED]

[REDACTED]

[REDACTED]

[REDACTED]

[REDACTED]

[REDACTED]

[REDACTED]

[REDACTED]

[REDACTED]

[REDACTED]

[REDACTED]

[REDACTED]

[REDACTED]

[REDACTED]

[REDACTED]

#### **7.4 PATIENT PROFILE**

Subject profiles will be used to further explore the biological activity of CVC. The subject profiles will contain stick plots of ALP over time, plotted simultaneously with ALT over time. Demographic and baseline factors that will appear in the figure will include the following: age, sex, race, type of IBD, Partial Mayo Risk score at the screening visit, and treatment-emergent serious adverse events (SAEs).

#### **8.0 EVALUATION OF SAFETY PARAMETERS**

The safety analysis will be performed using the safety analysis set. The safety parameters will include AEs, clinical laboratory parameters, vital signs, and ECG parameters.

The safety endpoints to be summarized are as follows:

- Evaluation of the safety and tolerability of CVC through 24 weeks of treatment in adult subjects with PSC
- Evaluation of the proportion of subjects with a treatment-emergent adverse event (TEAE) or a clinically significant laboratory abnormality (overall and of any given type)
- Evaluation of the proportion of subjects who discontinue due to an AE
- Evaluation of AEs, clinical laboratory tests, physical examination, and 12-lead ECG

Unless otherwise specified, safety will be evaluated using the safety analysis set and will be presented in appropriate listings and frequency tables.

## 8.1 ADVERSE EVENTS

An *adverse event* is defined as any untoward medical occurrence in a subject or clinical investigation subject administered a pharmaceutical product and which does not necessarily have a causal relationship with this treatment. An AE can therefore be any unfavorable and unintended sign (including an abnormal laboratory finding), symptom, or disease temporally associated with the use of a medicinal (investigational) product, regardless of whether related to the medicinal (investigational) product.

Verbatim descriptions of AEs will be coded by using Medical Dictionary for Regulatory Activities (MedDRA), Version 18.1 or later. The investigator will assess the grade for each AE and SAE reported during the study.

The AE severity will be graded according to the scale below, in addition to the National Cancer Institute Common Terminology Criteria for Adverse Events (NCI CTCAE), Version 4.03, Table for Grading the Severity of Adult Adverse Events. The clinical significance of the AE is determined by the investigator.

- Grade 1 (mild): asymptomatic or mild symptoms; clinical or diagnostic observations only; intervention not indicated

- Grade 2 (moderate): minimal, local or noninvasive intervention indicated; limiting age-appropriate instrumental activities of daily living (ADL)
- Grade 3 (severe): medically significant but not immediately life-threatening; hospitalization or prolongation of hospitalization indicated; disabling; limiting self-care ADL
- Grade 4 (life-threatening): life-threatening consequences; urgent intervention indicated
- Grade 5 (death): death related to AE

### 8.1.1 Serious Adverse Events

An AE or suspected adverse reaction is considered serious if, in the view of either the investigator or sponsor, it results in any of the following outcomes:

- Death
- Life-threatening AE (An AE or suspected AE is considered life-threatening if, in the view of either the investigator or sponsor, its occurrence places the patient or subject at immediate risk of death. It does not include an AE or suspected adverse reaction that, had it occurred in a more severe form, might have caused death.)
- Inpatient hospitalization (i.e., admission, overnight stay) or prolongation of existing hospitalization
- Persistent or significant incapacity or substantial disruption of the ability to conduct normal life functions
- Congenital anomaly/birth defect
- Important medical events (An important medical event is one that, when based upon appropriate medical judgment, may jeopardize the subject and may require medical or surgical intervention to prevent one of the outcomes listed above in the definition of an SAE. Examples of such events include allergic bronchospasm requiring intensive treatment at an emergency room or at home, blood dyscrasias, convulsions that do not result in inpatient hospitalization, or the development of drug dependency or drug abuse.)

A *treatment-emergent adverse event* is defined as any AE (classified by preferred term [PT]) not present before the first dose of the study medication or any adverse event already present that worsens in severity grade after the first dose of the study drug. If more than one AE is reported before the first dose of the study medication and coded to the same PT, then the AE with the greatest severity will be used as the benchmark for comparison to the AEs occurring during the study that were also coded to that PT. Dates and times for AEs will not be imputed. AEs with a missing start date or time that leads to ambiguity about whether the AE is treatment emergent will be considered treatment emergent.

The incidence of TEAEs will be summarized overall by system organ class (SOC) and PT. For each level of SOC and PT, a subject will be counted only once for the purpose of summarization.

The incidence of treatment-emergent SAEs, TEAEs leading to study drug discontinuation, and TEAEs related to study drug will be summarized by SOC and PT.

A summary of TEAEs occurring in 5% or more of subjects will be reported by SOC and PT, and information can be extracted from the main TEAE incidence table.

Separate summaries will be presented for Grade 3 toxicities resulting in study drug interruption by SOC and PT and for Grade 4 toxicities resulting in study drug discontinuation by SOC and PT.

In the summary tables (except the summaries of the TEAEs reported by maximum severity) the number and percentage of subjects reporting at least one TEAE will be presented, followed by the number of events. For each SOC, the number and percentage of subjects reporting one or more TEAEs within that SOC will be reported. Then, each PT within that SOC will be reported, showing number and percentage of subjects reporting at least one TEAE classified as that particular PT. The summary will be produced at the SOC level according to the MedDRA internationally agreed sorting order, and then within the SOC by descending frequency at the PT level.

For the summary of TEAE by maximum severity grade, if a subject has more than one event with different severities within a given PT, then the most severe event will be included in the table. Within each SOC, each TEAE listed by PT will have up to five associated rows, one for each observed severity grade. The number and

percentage of subjects who have at least one TEAE with that PT at that greatest severity will be shown. If a subject had more than one TEAE mapped to the same PT, then that TEAE will be represented according to the corresponding maximal level of severity.

[REDACTED]

[REDACTED]

- [REDACTED]
- [REDACTED]
- [REDACTED]
- [REDACTED]
- [REDACTED]

[REDACTED]

[REDACTED]

[REDACTED]

[REDACTED]

[REDACTED]

[REDACTED]

[REDACTED]

[REDACTED]

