### 7.1 Overall Study Design and Plan

This is a Phase 2, single-arm, open label, proof of concept study of CVC in approximately 25 adult subjects with PSC. [REDACTED]

Screening will occur within 6 weeks before the Baseline Visit. Subjects will review the ICF and provide written consent before any screening procedures taking place. After completing Screening visit, eligible subjects can be scheduled for study enrollment. At the Baseline Visit, subjects who have met all the eligibility criteria will be enrolled in the study and begin treatment with CVC. Subjects will return to the study site for on-treatment evaluations at Weeks 4, 8, 12, 16 and 24. Approximately 4 weeks after the last dose of study drug (Week 28), subjects will undergo follow-up evaluations. Subjects who discontinue study drug prior to completion of 24 weeks of treatment will be required to return to the clinic for an Early Discontinuation Visit.

The study design is illustrated in [Figure 7-1](#).

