## 10.0 STUDY PROCEDURES

Study procedures are summarized across all study visits within the Schedule of Assessments (Table 20-1).

Subjects should refrain from strenuous physical activity (e.g., weight lifting, strenuous yard work, intensive exercise workouts) for 48 hours prior to study visits and laboratory evaluations.

For IBD subjects only: Eligible subjects will be required to complete a diary daily to assess stool frequency and blood in the stool (Partial Mayo Risk score), daily. In addition, the diary will include a question regarding abdominal pain in order to assess if the subject develops any significant increase in abdominal pain. If a subject exceeds a Partial Mayo Risk score of 4 at any time, by investigator assessment of patient diary as well as subject evaluation, then the subject will be reevaluated for his or her IBD at the clinical research site. Should subjects experience an increase in abdominal pain, stool frequency or blood in their stool between visits, they will be instructed to contact the site immediately for clinical assessment for their IBD.

The principal investigator or delegate will be instructed to inquire about abdominal pain at each study visit. As with all adverse events, any abdominal pain will be assessed for severity and causality by the investigator in the eCRF, per Section 11.4.

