**11.4.1.6 Follow-up of AEs and SAEs**

AEs (including SAEs) will be collected from the time of informed consent, throughout the treatment period, until 28 days after the last dose of study medication is administered.

All subjects who have AEs, whether considered associated with the use of the investigational product or not, must be monitored to determine the outcome. The clinical course of the AE will be followed up according to accepted standards of medical practice, even after the end of the period of observation, until a satisfactory explanation is found or the investigator considers it medically justifiable to terminate follow-up. Should the AE result in death, a full pathologist's report should be supplied if and when available.

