## ***12.5.2 Methods of Analysis for Safety Endpoints***

### **12.5.2.1 Adverse Events**

AEs will be tabulated by the MedDRA preferred term and system-organ classification. The occurrence of TEAEs will be summarized by treatment group using MedDRA preferred terms, system organ classifications, and severity (see Sections [11.4.1.3](#) and [11.4.1.4](#)).

All AEs will be listed for individual subjects showing both verbatim and preferred terms. Separate summaries of treatment-emergent SAEs and TEAEs related to study drug will be generated.

Any event reported on the CRF that occurs on or after the initiation of study drug is defined as treatment-emergent. Additionally, it is assumed that an AE that was reported to have started on Day 1 without an associated onset time may have occurred after the initiation of study drug. Hence, AEs occurring on Day 1 with no associated onset time are assumed to be treatment-emergent.

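### SAP 8.1.1 narrows the protocol's definition of a treatment-emergent AE without saying so: a new on-drug episode can go uncounted because the same preferred term was reported, and had resolved, before first dose

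*SAP*

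**What the plan says.** Protocol 12.5.2.1 uses onset alone: "Any event reported on the CRF that occurs on or after the initiation of study drug is defined as treatment-emergent". It makes no comparison with earlier events.

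SAP 8.1.1 has two limbs. The first admits "any AE (classified by preferred term [PT]) not present before the first dose of the study medication". The second admits "any adverse event already present that worsens in severity grade after the first dose of the study drug". A benchmark sentence follows. It opens "If more than one AE is reported before the first dose of the study medication and coded to the same PT" and continues that "the AE with the greatest severity will be used as the benchmark for comparison to the AEs occurring during the study", limited to later AEs with that same term. The section also counts as treatment-emergent any AE whose missing start date or time leaves its status unclear.

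SAP 1.7 states that the SAP takes precedence over analyses specified in the protocol, so the SAP rule is the one that would be programmed. SAP 2.1.2 openly records the sponsor's departure from the protocol on the per protocol set. The readable SAP text contains no such note about the TEAE definition.

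**The concern.** The SAP's comparison reaches AEs that were merely reported before dosing, whether or not they were still present on Day 1. Comparing grades is ordinary practice for an event ongoing at first dose, because only worsening is then informative. For an event that has resolved, a later episode is a new occurrence on drug, and the protocol counts it.

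Pre-dose AEs will exist in the data. Protocol 11.4.1.6 says "AEs (including SAEs) will be collected from the time of informed consent, throughout the treatment period", and Protocol 7.1 says "Screening will occur within 6 weeks before the Baseline Visit". The symptoms most likely to appear both before and after dosing are those the protocol watches closely: investigators "will be instructed to inquire about abdominal pain at each study visit", and subjects with IBD keep a daily diary (Protocol 10.0).

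The proportion of subjects with a TEAE, overall and of any given type, is a stated safety endpoint (Protocol 6.0, SAP 8.0). The trial has one arm, so there is no control rate that would carry the same undercount.

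**Working it through.** The plan gives no figure to reproduce. The check sets the two definitions side by side and then scales the effect of one reclassified subject.

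**Step 1. Apply both rules to the same histories (one preferred term, one subject).**

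| Before first dose | On drug | Protocol 12.5.2.1 | SAP 8.1.1 as worded |
|---|---|---|---|
| None | Any grade | TEAE | TEAE |
| Grade 1, resolved | New episode, Grade 2 | TEAE | TEAE (grade rose) |
| Grade 2, resolved | New episode, Grade 2 | TEAE | Not a TEAE |
| Grades 1 and 3, resolved | New episode, Grade 2 or 3 | TEAE | Not a TEAE (benchmark is Grade 3) |
| Grade 1, ongoing | Same event worsens to Grade 2 | Not addressed | TEAE |
| Start date missing, status unclear | – | Addressed only for Day 1 onset without a time | TEAE |

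Rows 3 and 4 are the problem. Rows 5 and 6 show that the SAP can also count more than the protocol does.

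**Step 2. Identify which sentence excludes the event.** In row 4 it is the benchmark sentence, which speaks of AEs reported before first dose and so includes resolved ones. In row 3 there is only one pre-dose AE, so the benchmark sentence is not triggered. There the two limbs do the excluding: the term was present before dosing, and the grade did not rise. If presence is taken to mean ongoing at first dose, row 3 becomes a TEAE. On that reading one resolved episode would not block a recurrence while two would, which is hard to defend as intended.

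**Step 3. Trace the effect.** SAP 8.1.1 builds the tables of treatment-emergent SAEs, TEAEs leading to discontinuation and related TEAEs on the same definition. The benchmark compares grade, but seriousness is defined by outcome. A non-serious Grade 3 event before dosing could therefore keep a new Grade 3 SAE of the same term out of the treatment-emergent SAE table.

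**Step 4. Scale.** Planned N is about 25 (SAP 1.4).
- One subject reclassified: 1/25 = 4.0 percentage points on that preferred-term row.
- The SAP's table of TEAEs in 5% or more of subjects needs 0.05 × 25 = 1.25, so 2 subjects. A term with 2/25 = 8.0% that loses one subject falls to 1/25 = 4.0% and leaves that table.
- Overall proportion with any TEAE: unchanged unless the affected subject has no other TEAE.
- Number of subjects affected: not given, and not derivable from the documents. Zero is possible.

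**The case against.** The SAP is entitled to refine the protocol's analyses and says that it does. Only one of the two rules is in force, so this is an unexplained narrowing and not a live contradiction. That is correct, but it does not explain why resolved events should set a benchmark.

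The benchmark sentence covers only two or more pre-dose AEs of one term, and the wording for a single AE is open to an ongoing-at-baseline reading. This stands. The classification by preferred term favours the narrower count, but the text does not settle it.

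The dropped events are not lost. Protocol 12.5.2.1 lists all AEs by subject, SAP 3.1 promises data listings, and SAP 8.1.1 adds summaries of Grade 3 toxicities causing interruption and Grade 4 toxicities causing discontinuation. Part of the SAP's AE text is redacted, so other displays may exist. In a study of 25 subjects listings can be read in full. This limits the harm, but a listing does not correct an incidence table for a stated endpoint.

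Eligibility also works against pre-dose episodes: entry requires a Partial Mayo score of 0 to 3 and no recent colitis flare needing intensified therapy (Protocol 8.2 and 8.3). The frequency may therefore be low.

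A reader might infer that the SAP definition always favours the drug. It does not, because its worsening limb and its rule for ambiguous dates can raise counts. A reader might also assume several affected subjects and derive a large undercount, or apply it to the overall TEAE proportion. The documents give no rate to support the first, and one preferred-term row does not translate into the second.

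**Conclusion.** The concern holds in limited form. As worded, SAP 8.1.1 leaves out a new on-drug episode of equal or lower grade when the same preferred term was reported and resolved before first dose. The protocol counts that episode, and the SAP neither states nor justifies the change. With two or more such pre-dose AEs the exclusion is explicit. With one, it depends on presence not meaning ongoing at first dose.

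The size is about 4 percentage points per affected subject on a single preferred-term row, assuming 25 subjects in the safety set, with an unknown and possibly zero number affected. The error sits in the incidence tables, not in the recorded data. It should be corrected because it concerns a stated safety endpoint.

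**What to change.** In SAP 8.1.1, define a TEAE as any AE with onset on or after first dose (the protocol's rule), plus any AE ongoing at first dose that worsens in grade afterwards. Apply the grade benchmark only to AEs ongoing at first dose. Keep the rule that ambiguous dates count as treatment-emergent.

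State also where the pre-dose grade comes from. SAP 5.2 places pre-treatment AEs in medical history and lists their term, dates and ongoing status, but no grade.

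If the sponsor prefers the present rule, the SAP should record the departure, give the reason, and add a TEAE table under the protocol definition.

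The cost is a sentence or two in the SAP, a small programming change using onset and end dates already collected, and slightly higher TEAE counts. No new data are needed.
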